## Protocol

- Use the section headings to write the Protocol, inserting the appropriate material in each. If a section is not applicable, leave heading in and insert N/A.
- When submitting Protocol (new or revised), enter the date and version number to the field at the top of Protocol.

\*\*\*\*\*

### 1. Abstract

Alcohol use disorders (AUDs) are prevalent among Veterans and result in significant physical and psychological burden. Among those who receive treatment for AUDs, 1 in 3 relapses to problematic drinking within one year of treatment. Thus, additional strategies are needed to enhance alcohol treatment outcomes. One promising approach involves providing concurrent treatment for a common complaint – difficulty falling or staying asleep. Up to 74% of Veterans seeking treatment for AUD report co-occurring symptoms of insomnia. Given the negative impact of insomnia on attention and emotion regulation, insomnia symptoms may decrease patients' abilities to attend to alcohol treatment and manage negative emotions that lead to craving and relapse. Moreover, approximately 50% of individuals with AUDs report using alcohol to help them sleep, making relapse more likely for those with no other tools or skills to help them sleep. Indeed, sleep disturbance has been identified as a risk factor for relapse among individuals in alcohol treatment. Thus, effective treatment of sleep problems may enhance alcohol treatment. Cognitive Behavioral Therapy for Insomnia (CBT-I) has been effective in reducing insomnia severity in individuals with AUDs; however, no investigations have examined the efficacy of CBT-I delivered concurrently with AUD treatment to determine its impact on treatment outcomes. This R21 aims to examine the feasibility, acceptability, and initial efficacy of a CBT-I supplement to outpatient alcohol treatment. A randomized pilot trial with 80 Veterans who meet diagnostic criteria for AUD and Insomnia Disorder will be conducted. Participants will be randomly assigned to receive Cognitive Behavioral Therapy for Insomnia (CBT-I) or minimal treatment (sleep hygiene handout only; SH) in addition to alcohol treatment as usual. Outcomes will be assessed at the end of the active intervention period (6 weeks) and 6 weeks post-intervention. Outcomes of interest include recruitment/retention rates, treatment satisfaction, insomnia severity, use of alcohol as a sleep aid, percentage of heavy-drinking days, and alcohol-related problems. Analyses will focus on size of treatment effects. This study will provide initial evidence that treatment of insomnia not only improves sleep but also allows participants to derive greater benefit from outpatient alcohol treatment.

### 2. Objectives (include all primary and secondary objectives)

- (1) To test the feasibility and acceptability of a CBT-I supplement to outpatient alcohol treatment.
- (2) To evaluate the initial efficacy of the CBT-I supplement on alcohol use outcomes.

### 3. Background

Up to 74% of Veterans seeking treatment for alcohol use disorder (AUD) report symptoms of insomnia. These symptoms represent a **barrier to alcohol treatment** for three distinct reasons. First (1), approximately 50% of individuals with alcohol use disorders report using alcohol to help them sleep; thus, those without alternative sleep aids may relapse to drinking if insomnia persists. Insomnia symptoms have also been associated with significant deficits in (2) attention/working memory and (3) emotion regulation. Because cognitive-behavioral alcohol therapies (CBT) capitalize on individuals' use of these abilities to identify and adapt to the stimuli that lead to alcohol use, CBT-based treatments may have limited effectiveness for patients

with insomnia. This combination of factors – continued insomnia and limited cognitive/emotional capacity to respond to treatment – may explain in part why insomnia symptoms precipitate relapse among the 1 in 3 individuals who relapse to problematic drinking within one year of alcohol treatment.

Cognitive Behavioral Therapy (CBT-I) is the first line of treatment for insomnia. It has been associated with moderate to large improvements in insomnia outcomes, with effects maintained 24 months after treatment. It has been effective in reducing insomnia severity and sleep complaints among U.S. military Veterans, including those with comorbid PTSD and depression. It has also been effective in reducing symptoms of insomnia – but not subsequent rates of relapse – among alcohol dependent individuals with 1+ months of sobriety. However, **no research has examined the impact of CBT-I among individuals actively engaged in alcohol treatment.** Improving sleep is expected to enhance the efficacy of alcohol treatment among Veterans by enhancing their abilities to attend to treatment, regulate their emotions, and initiate sleep without alcohol.

Consistent with PA-18-202, the proposed R21 aims to examine the feasibility, acceptability, and initial efficacy of a CBT-I supplement to outpatient alcohol treatment. The **primary objective** of this study is to enhance alcohol treatment to account for the unique needs of Veterans with sleep disorders. We propose a 6-week randomized trial, in which 80 Veterans will be randomly assigned to receive Cognitive Behavioral Therapy for Insomnia (CBT-I) or minimal treatment (sleep hygiene only; SH) in addition to treatment as usual. Individuals participating in the Addictions Treatment Program at the Truman VA will be eligible to participate if they meet DSM-5 criteria for AUD and the episodic criterion ( $\geq 1$  mo) for Insomnia Disorder. Participants will complete assessments at baseline, post-treatment, and 6-week follow-up. We propose the following specific aims:

**Aim 1: To test the feasibility and acceptability of CBT-I delivered concurrently with alcohol treatment.** Recruitment (anticipated enrollment of at least 2 Veterans per month) and retention rates (goal  $\geq 70\%$  complete 6/6 treatment sessions) will indicate feasibility of the intervention. Treatment satisfaction (average score  $\geq 3$ , indicating ‘mostly satisfied’) will serve as an indicator of acceptability. Retention and satisfaction will be measured separately for insomnia and alcohol treatments.

**Aim 2: To evaluate the initial efficacy of CBT-I on insomnia and alcohol use outcomes.** We hypothesize that Veterans receiving CBT-I will demonstrate greater improvements in insomnia severity, sleep efficiency, use of alcohol as a sleep aid, percentage of heavy-drinking days, and alcohol-related problems post-treatment and at 6-week follow-up.

**Aim 3 (exploratory): To examine proximal intervention outcomes.** We hypothesize that Veterans receiving CBT-I will demonstrate greater post-treatment improvements in attention (vigilance), working memory, treatment-related learning, negative affect, and emotion regulation.

#### 4. Study Procedures

This study will examine the feasibility, acceptability, and initial efficacy of Cognitive Behavioral Therapy for Insomnia (CBT-I) delivered concurrently with CBT for AUD using a randomized, parallel, two-group design (see Figure 1). Eighty Veterans will be randomly assigned to either **CBT-I** or a sleep hygiene education control (**SH**). All outcomes will be assessed at baseline, post-treatment, and 6-week follow-up. This design will allow us to test the feasibility and acceptability of CBT-I among those in treatment for AUD (**Aim 1**); evaluate the initial efficacy of CBT-I in improving insomnia and alcohol-related outcomes (**Aim 2**); and examine CBT-I effects on attention, working memory, learning, negative affect, and emotion regulation, which may be examined as mediators in a subsequent trial (**Aim 3**).

**Study site.** Participants will be recruited through the Addictions Treatment Program at the Harry S. Truman Memorial Veterans Hospital (Truman VA) in Columbia, MO. We will recruit 115 participants over 20 months (see Table 2) to obtain a final sample of at least 80 participants.

[figure not shown]
**Participants.** Patients in the Addictions Treatment Program at the Truman VA will be **included** if they meet DSM-5 criteria for Alcohol Use Disorder and the episodic criterion ( $\geq 1$  mo) for Insomnia Disorder. **Criteria for AUD** include 2+ symptoms in the past 12 months that result in distress or impairment related to alcohol use (e.g., using more than intended, unsuccessful attempts to cut down). **Criteria for insomnia** include difficulty ( $>30$ min) falling asleep, staying asleep, or waking up too early on 3+ nights per week despite adequate opportunity and circumstances for sleep; and daytime impairment in mood, cognitive, social, or occupational activities. Participants will be **excluded** if they are unable to provide informed consent, demonstrate cognitive impairment, report continuous sobriety for more than 2 months at baseline assessment, report a manic episode or seizure (contraindications for sleep restriction) in the past year, have a severe psychiatric disorder that requires immediate clinical attention (e.g., psychosis, suicidal ideation with intent and plan), or began a new sleep medication in the past 6 weeks. Consistent with standard practice, those who endorse symptoms of sleep-related breathing disorders ( $\geq 2/8$  symptoms on the STOP-BANG), restless leg syndrome, periodic limb movement disorder, or narcolepsy will be referred for overnight polysomnography.

**Recruitment and initial screening.** Patients in the Addictions Treatment Program (ATP) at the Truman VA will be recruited via flyers and provider referral. All residential patients at the ATP will receive a flyer about the study and complete a brief (9-item) screener for the study as part of the intake process. Providers will share the de-identified results of the screener with PI [name]. If participants are interested in the study, they may contact the research team directly. However, to decrease burden on both providers and participants, providers will also have the option of providing the research team with contact information for patients who may be eligible and interested. The research team will then reach out to the patient directly to assess their interest in participating. Research staff will reach out to potential participants three times by phone. Research staff will also attend the beginning of treatment groups/meetings in order to inform individuals about the study and answer any questions they may have. PI [name] will participate in weekly behavioral health team meetings to facilitate the screening and recruitment process (i.e., reminding them about the study, updating them on recruitment progress, and answering any questions).

**Phone screening.** A research assistant (RA) will share more details about the study and conduct a brief eligibility screen ( $\sim 15$ min) with the potential participant in person or over the phone (see Table 1). Those who screen eligible will be scheduled for baseline.

**Baseline assessment.** Participants will provide written informed consent prior to completion of baseline (see Table 1). In the case of remote baseline assessments, an RA will walk the participant through an electronic version of the written consent form, which they will be asked to sign electronically via the Qualtrics platform. The RA will then print and sign the electronic version of the participant's consent. The baseline evaluation will involve assessment of substance use and sleep disorders and full eligibility criteria using the Mini International Neuropsychiatric Interview (MINI) 7.0.2. Consistent with standard practice, those who endorse symptoms of sleep-related breathing disorders, restless legs syndrome, periodic limb movement disorder, or narcolepsy will be referred for polysomnography. Given the prevalence of sleep apnea in this population, individuals who meet all eligibility criteria but report symptoms of sleep apnea will complete one night of holter monitoring (using an Evo Holter Recorder, SpaceLabs Healthcare) at home in their own beds to rule out for sleep apnea.

Eligible participants will complete baseline assessment measures and will be randomly assigned to either the CBT-I or SH condition. Participants in both conditions will be oriented to the prospective sleep diary, which

they will be asked to complete every morning for the next 6 weeks. The RA will provide all participants with a general handout on sleep hygiene (from the National Sleep Foundation website) and answer any questions they may have about the guidelines.

To confirm diagnosis of insomnia, all eligible participants will complete one week of daily sleep diaries (between baseline and treatment session 1), which will be collected electronically and time-stamped each morning using the Qualtrics data management system. Participants who have not completed the diary each morning by noon will receive a reminder text or phone call from study staff. Sleep diaries measure sleep onset latency, wake after sleep onset, total sleep time, sleep efficiency, and sleep quality. In this study, sleep diaries will also assess use of sleep medication and use of alcohol/other drugs (yes/no) to help with sleep. Sleep medication variables will include name, dosage, and time taken and will be converted to lowest recommended dosage units for data analysis. Participants who are unable to complete the daily sleep diaries by computer or phone will be provided with pen-and-paper surveys to fill out each day by hand.

*Follow-up.* Follow-up assessments (see Table 1) will be administered in person by the RA, who will be blind to participant condition. Upon completion of the study, SH participants will be offered a referral for CBT-I, which is available with trained providers at the VA.

*Remote appointments.* If needed, treatment and follow-up appointments may be completed remotely using Zoom Pro or the VA's Video Connect service. Using their VA email from the VA laptops, research staff would send the participant a link to launch the session. Participants wanting to use their iPhone or iPad for the session would have to download the VA Video Connect application onto their device. On all other devices (e.g., PCs, laptops, Android devices), the participant will simply open the email and click the link to launch the secure video session. This service uses encryption to ensure that sessions are private and secure and is designed for Veterans in rural areas with limited access to healthcare facilities.

*Retention strategies.* To enhance follow-up rates, participants will receive:

- Up to \$40 for baseline (~2hr): \$10 for completing the assessment, \$10 for completing all seven daily surveys, and \$20 for returning the actiwatch.
- Up to \$50 for the post-treatment assessment (~1hr): \$40 for completing the assessment and \$10 for completing all seven daily surveys
- Up to \$60 for the 6-week follow-up (~1hr): \$50 for completing the assessment and \$10 for completing all seven daily surveys

Participants will also receive reminder texts/calls, have access to free parking, and receive treatment at no cost.

*Cognitive Behavioral Therapy for Insomnia (CBT-I).* CBT-I will be delivered individually, in person, in five weekly one-hour sessions. A sixth week of treatment will be included – and scheduled for the same date as the post-treatment assessment – if the participant and research team agree that it would be beneficial (e.g., if a participant has difficulty grasping cognitive therapy concepts). Study therapists will follow the 2014 CBT-I in Veterans manual developed by leading researchers in the behavioral sleep medicine field (see Table 3). Intervention components include (1) sleep hygiene: limiting naps; avoiding caffeine, tobacco, alcohol, and rich/heavy foods before bedtime; exercising; establishing a bedtime routine; and creating a comfortable sleep

Table 1. *Assessment, therapy, and payment schedule*

Week	Assmt	CBT-I	Paymt	Bonus
1	BL		10	
2		S1	20	10
3		S2		
4		S3		
5		S4		
6		S5		
7	Post-tx	(S6)	40	
8				10
9				
10				
11				
12	1mo		50	
13				10

*Note.* 1mo = 1 month. Assmt = assessment. BL = baseline. Bonus = bonus payment for completion of all 7 daily surveys. Paymt = standard payment. Tx = treatment.

environment; (2) sleep restriction: limiting time in bed in order to improve sleep efficiency, or the percentage of time in bed that is actually spent sleeping; time in bed will be titrated each week based on sleep efficiency; (3) stimulus control: strengthening association between bedroom and sleep to decrease conditioned arousal; (4) relaxation: diaphragmatic breathing, progressive muscle relaxation, and visual imagery to reduce arousal; and (5) cognitive therapy: identifying and challenging thoughts that interfere with sleep.

*Sleep hygiene (SH).* All participants will receive a one-page handout on sleep hygiene. This is the only intervention that participants assigned to the SH condition will receive and is consistent with what may be expected as standard care in a doctor's visit with a primary care physician.

Table 2. Survey Instruments and Schedule of Administration

Use	Construct	Measure(s)	Cut-score		
Use	Construct	Measure(s)	BL	Post	6wk
Screen	Insomnia severity , past 2 weeks	Insomnia Severity Index (Morin et al., 2011)		≤ 9 excluded at phone screen	
	Sleep apnea , past month	STOP questionnaire (Chung et al., 2008)		≥ 3 excluded at phone screen	
Use	Construct	Measure(s)	BL	Post	6wk
Cov	Demographics	See instruments	X		
	Other drug use , past 6 weeks	Drug Use Screening Inventory	X	X	X
	Use of sleep medication	Daily Sleep Diary (Carney et al., 2012)	X	X	X
Aim 1	Recruitment	Completion of ≥ 1 session of CBT-I		X	
	Retention	Completion of 6/6 sessions of CBT-I		X	
	Treatment satisfaction , measured separately for CBT-I and CBT-AUD	Client Satisfaction Questionnaire (Larsen et al., 1979)			X
Aim 2	% abstinent days , past 6 weeks	Timeline Follow-back (TLFB) for alcohol (Sobell & Sobell, 1996)	X	X	X
	% heavy-drinking days (≥4/5 drinks/day for women/men)				
	Alcohol problems , past 6 weeks	Short Inventory of Problems ([name] et al., 1995)	X	X	X
	Use of alcohol or other drugs to help with sleep , past 6 weeks	Daily Sleep Diary (Carney et al., 2012)	X	X	X
	Insomnia severity , past 2 weeks	Insomnia Severity Index (Morin et al., 2011)	X	X	X
	Total wake time , average past week	Daily Sleep Diary (Carney et al., 2012)	X	X	X
	Sleep quality , average past week	Daily Sleep Diary (Carney et al., 2012)	X	X	X
	Dysfunctional beliefs, past month	Dysfunctional Beliefs about Sleep Scale	X	X	X
Aim 3	Treatment-related learning	Project SAVE Alcohol Quiz Project SAVE Alcohol Vignette	X	X	X
	Executive functioning	Psychomotor Vigilance Task (Dinges et al., 1985) N-back Task (Schmiedek et al., 2014) Monetary Choice Questionnaire UPPS Measure of Impulsivity Cognitive Failures Questionnaire	X	X	X
	Negative affect , past week	Positive and Negative Affect Schedule	X	X	X
	Emotion regulation , past 30 days	Brief Difficulties in Emotion Regulation Scale (Bjureberg et al., 2016)	X	X	X
	Alcohol craving , past week	Penn Alcohol Craving Scale	X	X	X
	Mental health symptoms	PTSD Checklist for DSM-5 Patient Health Questionnaire-9 for depression GAD-7 measure of anxiety Satisfaction with Life Scale	X	X	X

*Note.* BL=baseline. Cov = potential covariates. Post = post treatment. Wk = week.

*Blinding.* PI [name] will not be blinded to block size or participant assignment because she will inform study therapists of participant assignment to conditions. However, PI [name] and study therapists will be blinded to assessment outcomes, and the assessment RA will be blinded to participant condition.

*Treatment integrity.* Treatment integrity will be assured in three steps. (1) Delivery. The study therapist will receive training in use of the treatment manual via audio-recorded mock therapy sessions. PI [name] and co-I [name], both of whom are licensed clinical psychologists, will evaluate audiotapes of mock sessions and provide corrective feedback. All intervention sessions will be audio-recorded, given participant permission. PI [name] and co-I [name] will review session audiotapes for ongoing training and supervision. PI [name] will score five randomly selected tapes to assess treatment fidelity using a checklist of treatment elements. Descriptive analyses will be used to determine the proportion of intended treatment elements covered in intervention sessions. (2) Comprehension. Participants will be provided with a workbook detailing treatment instructions, rationale, and handouts and encouraged to ask questions. (3) Enactment. Workbooks will contain written instructions on home assignments, and therapists will encourage assignment completion.

*Early termination.* All participants will receive sleep hygiene recommendations immediately following baseline assessment, so every participant who attends baseline will receive some form of treatment for insomnia. However, participants may decide to stop participating in the study at any time without penalty. If they decide to withdraw their participation, therapy will be terminated. This will be discussed as part of the informed consent process.

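### Randomisation appears to come before the diary week that is meant to confirm insomnia and that supplies the diary baseline used for adjustment

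*Combined protocol and SAP*

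**What the plan says.** In Section 4 (Baseline assessment), "Eligible participants will complete baseline assessment measures and will be randomly assigned to either the CBT-I or SH condition". The next sentence continues: "Participants in both conditions will be oriented to the prospective sleep diary", a diary to be kept each morning over the following six weeks. At the same contact, "The RA will provide all participants with a general handout on sleep hygiene". For the control arm, "This is the only intervention that participants assigned to the SH condition will receive", and the Early termination paragraph says that everyone gets this advice directly after the baseline assessment.

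The purpose of the first diary week comes immediately afterwards: "To confirm diagnosis of insomnia, all eligible participants will complete one week of daily sleep diaries (between baseline and treatment session 1". Table 1 puts the baseline visit in week 1 and session 1 in week 2. The baseline "bonus payment for completion of all 7 daily surveys" also falls in week 2.

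Table 2 names the daily diary as the baseline, post-treatment and follow-up source for total wake time and sleep quality, each defined as "average past week". It names the same diary for alcohol or drug use as a sleep aid, but with a six-week look-back. Section 7 lists all three among seven Aim 2 primary outcomes, adjusts Cohen's d for baseline scores, and states an intent-to-treat analysis.

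**The concern.** Two things depend on whether the diary week falls before or after allocation.

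The first is the baseline. Adjustment for a covariate is safe when allocation cannot have influenced it. A self-reported diary kept after allocation does not have that protection. The Blinding paragraph covers the principal investigator, the therapists and the assessment RA, but not the participants. A participant who knows that therapy is about to begin, or that it is not, may sleep or report differently that week. The analysis would treat that reaction as a pre-existing difference and adjust for it. The abstract says the analyses will concentrate on the size of treatment effects, so a systematic shift in d matters even in a pilot.

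The second is eligibility. Insomnia Disorder is an inclusion criterion, and the diary is given a confirming role. If it fails to confirm, the person is already randomised. Removing them conflicts with intent-to-treat; keeping them means the check decides nothing. The plan does not say which applies.

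**Working it through.** **Order of events.** No sentence or Table 1 row dates randomisation, so the order has to be read from the sequence.

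- Assignment is mentioned before the diary, and those oriented to the diary are already described as belonging to a condition.
- The diary is prospective, so its entries come after that orientation.
- The confirming week lies between the visit (week 1) and session 1 (week 2), and its bonus falls in week 2.

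Together these give: visit, assignment, diary week, session 1.

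**Outcomes affected.** Of the seven Aim 2 primary outcomes, two (total wake time and sleep quality) clearly take their baseline from this week. The sleep-aid outcome is a third only if its baseline comes from the same diary. One week of prospective entries cannot cover a six-week look-back, so its source is unclear.

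**The plan's own figure.** The plan gives no figure on this point. The nearest is its power of .99 for f = .25 and N = 80. With assumed alpha 0.05, two groups and correlation 0.5, the noncentrality is f² × N × m / (1 − rho). For m = 2 time points this is 0.0625 × 80 × 2 / 0.5 = 20, giving power 0.993; for m = 3 it is 30, giving 0.999. The stated figure is reproduced and does not depend on the order of events.

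**Size of a baseline shift.** The documents give no rates, so the inputs are assumptions: a between-arm shift δ in the diary-week mean of 0.1, 0.2 or 0.3 SD; a baseline-to-outcome correlation ρ of 0.3, 0.5 or 0.7; equal SDs; and a reaction confined to the baseline week. The adjusted difference is the outcome difference minus ρ times the baseline difference, so it moves by ρ × δ in absolute size:

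| ρ | δ = 0.1 | δ = 0.2 | δ = 0.3 |
|---|---|---|---|
| 0.3 | 0.03 | 0.06 | 0.09 |
| 0.5 | 0.05 | 0.10 | 0.15 |
| 0.7 | 0.07 | 0.14 | 0.21 |

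A plain baseline-to-post change contrast would move by the full δ, 0.1 to 0.3.

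**Scale.** With 40 per arm the 95% half-width of d is about 1.96 × √(2/40) = 0.44. After adjustment it is 0.438 × √(1 − ρ²): 0.42 at ρ = 0.3, 0.38 at 0.5 and 0.31 at 0.7. The largest shift, 0.21, occurs at ρ = 0.7 and is about two-thirds of the half-width there (0.21 / 0.31).

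**Unconfirmed participants.** If an assumed 5%, 10% or 20% were not confirmed and were removed, 80 would fall to 76, 72 or 64. On the two-time-point calculation above, power would be 0.990, 0.987 or 0.976. Loss of power is therefore not the issue; the issue is whether the randomised groups stay intact.

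**The case against.** The strongest reply is that the order is inferred. Table 2 marks the diary as a baseline measure, the payment scheme counts the seven diaries as part of baseline, and the confirming diary is described for eligible rather than randomised participants. On that reading the diary comes first. This cannot be ruled out, but it fits poorly with orienting people already in a condition to a prospective diary. If it is what the sponsor intends, the text still needs changing, because staff following it in sequence would randomise first.

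A reader might infer several stronger claims that the documents do not support:

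- *That participants know their arm while keeping the baseline diary.* The plan does not say when they are told. The handout is the same for everyone, so receiving it need not reveal the arm. Knowledge is possible, because session 1 follows in week 2, but it is not documented.
- *That the plan excludes people after randomisation.* It does not say so. The baseline interview (MINI) assesses full eligibility, the diary is a second check, and intent-to-treat suggests that everyone stays. The gap is that no consequence is stated.
- *That removal would fall mainly on the CBT-I arm because "time in bed will be titrated each week based on sleep efficiency".* Both arms keep diaries for six weeks, and the confirming week ends before any titration. There is no basis for a one-arm removal scenario.
- *That the early handout biases the comparison.* It goes to both arms. It means only that neither arm has a diary baseline free of advice.

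It is also true that even the largest assumed shift is smaller than the random error in d. That limits the importance of the point but does not remove it, since a systematic shift does not average out.

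**Conclusion.** The point holds as a matter of sequence and of an unstated rule. As written, allocation appears to precede both the diary check on insomnia and the diary baseline for at least two of seven Aim 2 primary outcomes, or three if the sleep-aid baseline comes from the same week. A self-reported baseline recorded after allocation can carry an effect of knowing the arm into the adjusted effect size. On the assumed inputs that effect is 0.03 to 0.21 in d, with unknown direction; it is zero if participants do not learn their arm until the week is over. The documents support neither a claim that bias will occur nor a claim that anyone will be removed. The change is still worth making, because it removes both problems at little cost within the existing schedule.

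**What to change.** Keep the baseline visit and the sleep hygiene handout in week 1, as the Early termination paragraph promises. Run the seven-day diary. Randomise, and tell participants their arm, only after that week and before session 1 in week 2. Add the randomisation point to Table 1.

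State the diary's role. If it is an eligibility check, apply before allocation a rule that uses only what it records, for example onset latency or wake time after sleep onset above 30 minutes on at least 3 nights. It cannot carry the whole insomnia definition, since daytime impairment is not among its listed measures. If it is not a check, say that it is descriptive only. Either way, everyone randomised stays in the intent-to-treat analysis.

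The cost is about a week's delay in allocation, one added contact, and a therapist slot held and released if the person is assigned to SH. No new test or device is needed. Some people may drop out or be found ineligible before randomisation. At assumed non-confirmation of 5%, 10% or 20%, reaching 80 needs 80/0.95, 80/0.90 or 80/0.80, that is 85, 89 or 100 people entering the diary week. Section 4 plans to recruit 115 for a final 80 but does not say which losses the other 35 are meant to cover, so that margin should be checked.
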